NCT03781323

**Neoadjuvant FOLFOX therapy with Short Course Radiation and active surveillance in locally advanced
Rectal Cancer: A Phase II Study**

Version Date: 12/9/2019

Principal Investigator: [name]

Statistician: [name]

**Site: University of Rochester
James P. Wilmot Cancer Institute
[name]
[name]**

Figure 1. Schema

- Total number of patients enrolled to start chemotherapy, N=30
- All patients included in evaluation of complete clinical response, safety, toxicity, quality of life, and overall survival

[figure not shown]

Table of Contents

- 1.0 Purpose of Study and Rationale
 - 1.1 Purpose of Study
 - 1.2 Rationale
- 2.0 Study Objectives
 - 2.1 Primary Objective
 - 2.2 Secondary Objectives
- 3.0 Study Design
- 4.0 Selection Criteria
 - 4.1 Inclusion Criteria
 - 4.2 Exclusion Criteria
- 5.0 Methods and Study Procedures
 - 5.1 Subject Recruitment and Consent
 - 5.2 Pretreatment Evaluation
 - 5.3 Administration Schedule
 - 5.4 Disease Progression
 - 5.5 Posttreatment evaluation
 - 5.6 Discontinuation of Study
- 6.0 Schedule of Events
- 7.0 Treatment Dosing Modifications
- 8.0 Study Treatment Toxicities
 - 8.1 Oxaliplatin
 - 8.2 Leucovorin
 - 8.3 5-Flurouracil
- 9.0 Adverse Events Monitoring and Reporting
 - 9.1 Definition of Adverse Event
 - 9.2 Definition of Serious Adverse Event
 - 9.3 Reporting of Adverse Events
 - 9.4 Severity of Adverse Events
- 10.0 Objectives and Data Analysis
 - 10.1 Primary Endpoint
 - 10.2 Secondary Endpoints
 - 10.3 Data Analysis
- 11.0 Data Safety and Monitoring
- 12.0 Data Confidentiality and Storage
- 13.0 Data and Specimen Banking for Future Use
- 14.0 References

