To our knowledge, there are no studies currently evaluating a complete response to full, upfront neoadjuvant chemotherapy with mFOLFOX plus short course CT in locally advanced rectal adenocarcinoma followed by surveillance. From review of available literature, we conclude that there is the potential for an identifiable population of patients that may benefit from treatment with systemic therapy and short course RT with a complete or near complete response, while sparing these patients the toxicity of a total mesorectal excision. Earlier phase II studies demonstrate a range of complete response from 25% to 65% for total neoadjuvant therapy, but we conclude from these studies that the complete response rate is likely in the range of 30-40%.

In conclusion, we hypothesize that some patients with locally advanced rectal cancer with stage I (T2N)-IIIB disease (excluding clinical T4 or N2b staging) will benefit from our proposed protocol of total neoadjuvant therapy, with proposed reduction in surgical related toxicities.

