10.3 Data Analysis

We aim to accrue 40 participants over approximately a 5-year period. Though we hypothesize that this study will be of clinical benefit to those who may avoid surgical intervention, we have no knowledge that a similar study has been conducted. Thus, we aim to gain a preliminary estimate of the rate of locally advanced rectal cancer patients that can be spared surgical intervention through the use of neoadjuvant chemotherapy plus short course radiation. We anticipate a 30% rate of complete or near complete clinical response to neoadjuvant chemotherapy plus short course radiation at the post-radiation assessment. This rate will include subjects discontinuing mFOLFOX due to stable or progressive disease at the interval assessment or re-staging assessment in the denominator.

With an anticipated response rate of 30%, a sample size of 40 subjects produces a one-sided 95% lower-limit exact binomial confidence interval with a width of 13.4% (lower limit of 16.6%). The maximum width of a one-sided 95% lower-limit confidence interval with 40 subjects would be 16.1% when the response rate is 50%. We target the lower limit of the confidence interval to determine if this regimen demonstrates sufficient evidence of efficacy to be considered worthy of future study.

The complete or near complete response rate and associated 95% one-sided exact binomial confidence interval will be presented. Disease-free and overall survival will be described using the Kaplan-Meier method. Types and grades of adverse events will be tabulated. Changes in QOL (from baseline) will be described using means and standard deviations at each time point assessed. We will calculate these summary measures separately in those who obtain a complete or near complete response to up to 12 cycles of mFOLFOX and short course radiation and are entering watch and wait surveillance, and those who required surgery with or without radiation therapy prior to completion of mFOLFOX therapy. QOL will be measured using validated

QOL forms EORTC QLQ-30, and EORTC QLQ-CR29 as mentioned in Section 5.2, with paper-based surveys and scored according to the EORTC scoring manual [10].

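### The primary response rate is to be estimated but is given only a lower confidence limit; a two-sided 90% exact interval would keep that limit and add an upper one

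*Combined protocol and SAP*

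**What the plan says.** Section 10.3 (Data Analysis) describes the purpose as estimation: "we aim to gain a preliminary estimate of the rate of locally advanced rectal cancer patients" who can avoid surgery. Section 2.1 likewise makes the primary objective an assessment of the rate of complete or near complete response. The expected value appears twice. Section 1.2 concludes that "the complete response rate is likely in the range of 30-40" per cent, and Section 10.3 says "We anticipate a 30% rate of complete or near complete clinical response".

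The precision statement in Section 10.3 is based on a "one-sided 95% lower-limit exact binomial confidence interval" with 40 subjects, and the section explains why: the lower limit is what will be used to judge whether the regimen shows enough efficacy to be studied further. No threshold for that limit is given. The reporting sentence follows the same choice: "The complete or near complete response rate and associated 95% one-sided exact binomial confidence interval will be presented". Neither an upper limit nor a two-sided interval for the primary rate is planned anywhere in the document.

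The sample size is stated in two ways. Section 10.3 has "We aim to accrue 40 participants over approximately a 5-year period", and the schema (Figure 1) has "Total number of patients enrolled to start chemotherapy, N=30".

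**The concern.** A lower-limit interval extends to 100% by construction. It answers one question, how low the rate could plausibly be, and leaves open how high it could be. For a study meant to give a first estimate of a rate, that is half of the uncertainty statement.

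The missing half matters most if the result disappoints. The rationale expects 30-40%. If the observed rate falls well short, a reader will want to know whether the data rule that expectation out, and the planned interval cannot say so whatever is observed. The point estimate will be reported beside it, but it carries no statement of uncertainty above itself. What is at stake is the completeness of the primary report; the estimate and the use of the lower limit are not affected.

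**Working it through.** **Inputs.** Section 10.3: n = 40, anticipated rate 30% (12/40), one-sided 95% exact binomial lower limit. Figure 1: n = 30 (30% is 9/30). Section 1.2: expected range 30-40%.

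**Formulas (Clopper-Pearson).** For x responses in n, with probability a in a tail:
- lower limit = a-quantile of Beta(x, n − x + 1)
- upper limit = (1 − a)-quantile of Beta(x + 1, n − x)

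A one-sided 95% lower limit uses a = 0.05. A two-sided 90% interval uses a = 0.05 at each end. The lower-limit formula is therefore the same in both, and so is the result for the same data.

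**Step 1: the plan's printed figures.** Section 10.3 prints, for 40 subjects, a lower limit of 16.6% and width 13.4 points at a 30% rate, and a width of 16.1 points at 50%.

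| Calculation | Lower limit at 30% | Width at 30% | Width at 50% |
|---|---|---|---|
| Printed for n = 40 | 16.6% | 13.4 | 16.1 |
| One-sided 95% exact, n = 40 (12/40, 20/40) | 18.3% | 11.7 | 13.9 |
| One-sided 95% exact, n = 30 (9/30, 15/30) | 16.6% | 13.4 | 16.1 |
| Two-sided 95% exact, n = 40 | 16.6% | 13.4 | 16.2 |

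The printed figures are not reproduced with n = 40 and the stated method. All three match n = 30. A two-sided 95% interval at n = 40 matches the first two but misses the third in the last digit. As a check on the 18.3%: with p = 0.1831 and n = 40, P(X ≥ 12) = 0.05, as the definition requires.

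**Step 2: planned interval against the two-sided 90% interval.**

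| Responses | Estimate | Planned interval | Two-sided 90% exact |
|---|---|---|---|
| 6/40 | 15.0% | 6.7% to 100% | 6.7% to 27.5% |
| 12/40 | 30.0% | 18.3% to 100% | 18.3% to 44.0% |
| 20/40 | 50.0% | 36.1% to 100% | 36.1% to 63.9% |
| 9/30 | 30.0% | 16.6% to 100% | 16.6% to 46.5% |
| 15/30 | 50.0% | 33.9% to 100% | 33.9% to 66.1% |

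**Step 3: what each interval can say about 30-40%.**
- At 6/40 the two-sided interval lies wholly below 30%. At 7/40 its upper limit is 30.4%, so with n = 40 six responses or fewer would exclude the whole range. The planned interval contains all of 30-40% in these cases.
- At 12/40 both intervals contain all of 30-40%, so at the anticipated result the upper limit does not change the conclusion about that range.
- At 22/40 the lower limit is 40.9%, above the whole range. The planned interval can therefore show that the expectation was too low. Only the other direction is missing.

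**The case against.** The one-sided choice is deliberate, and the section explains it. Precision statement, intended use and reporting sentence all rest on the lower limit, so the plan is consistent in this respect, and a one-sided bound is a legitimate tool for a single-arm phase II screen. The endpoint is a single binomial proportion: once the count and denominator are reported, any reader can compute the upper limit. Changing the headline label from 95% to 90% also needs a word of explanation, and a two-sided 95% interval (16.6% to 46.5% at 12/40) would be another defensible choice.

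Most of this stands, and it is why the point is minor. What it does not answer is that the plan also declares an estimation aim. Fixing the level of the upper limit in advance costs one sentence and avoids choosing it after the data are seen.

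A reader might go further and infer that the trial could say nothing about whether 30-40% is compatible with its data. That is too strong, because the lower limit can contradict the range from below. A reader might also want the upper limit in order to rule out 65%, the top of the published range in Section 1.2. That section describes the 65% as a combined clinical and pathologic rate from one 34-patient study of a different regimen, and the protocol nowhere aims to test it. Nor do the documents say that a later trial would be planned from an upper limit; the only forward use they state is that of the lower one.

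**Conclusion.** The point holds as a free improvement in reporting. Section 10.3 states an estimation aim and plans an interval that is informative on one side only. A two-sided 90% exact interval contains everything the planned interval gives and adds an upper limit: 44.0% at 12/40, 27.5% at 6/40, 46.5% at 9/30. It would not be right to read this as an error in the analysis or as a fault in the one-sided use of the lower limit.

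Two conditions apply. First, the unchanged lower limit is the one computed from the same data. A reader might infer that the change preserves the printed 16.6% for 40 subjects. It does not: the one-sided 95% limit at 12/40 is 18.3%, and the printed 16.6% and 16.1 points together match 30 subjects. That discrepancy is separate and the more important of the two. Second, the response counts are illustrations. They assume that all 40 (or 30) subjects are in the denominator, in line with Section 10.3, which keeps in it those who stop mFOLFOX for stable or progressive disease.

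**What to change.** In Section 10.3, replace the reporting sentence with one to this effect: the response rate will be presented with its two-sided 90% exact (Clopper-Pearson) binomial interval, whose lower end is the one-sided 95% exact lower limit targeted in the sample-size paragraph. Keep that label wherever the result is reported, so that 90% is not taken for a weaker standard.

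The cost is one sentence. Sample size, data collection, patient management and the use of the lower limit stay as they are. When the section is opened for this edit, the sample size in Section 10.3 and Figure 1 should be reconciled and the printed limit and widths recomputed for whichever number the sponsor confirms.

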3.0 Study Design

This is a multi-center, phase II study investigating the efficacy of total neoadjuvant therapy with mFOLFOX and short course radiation and selective non-operative management in patients with locally advanced rectal cancer.

Participants with Stage IIA, IIIA, IIIB rectal adenocarcinomas, except for any T4 or N2b disease, who would otherwise undergo long course concurrent chemotherapy and radiation therapy followed by TME may be enrolled for treatment with mFOLFOX therapy. Participants with lower sphincter rectal cancer deemed not eligible for sphincter sparing surgery are not eligible for participation. Participants would be treated with up to 12 cycles of mFOLFOX therapy. (One cycle of mFOLFOX= 14 days) and short course radiation.

All patients will be evaluated once following six cycles of chemotherapy via endoscopy and CT plus MRI.

Patients with a partial, near or complete response will receive an additional 4-6 cycles of chemotherapy followed by reassessment.

Patients with stable or progressive disease defined as less than 20% reduction will be removed from study.

Following completion of all chemotherapy (10-12 cycles) patients will be re-assessed via endoscopy and CT plus MRI. Patients will then receive short course radiation followed by repeat assessment with endoscopy and CT/MRI. Those patients with evidence of complete or near complete clinical response following completion of all chemotherapy and radiation will be treated non-operatively and undergo close surveillance.

Patients with a partial response or stable disease will undergo TME.

Those with <20% response will be removed from study and undergo treatment per the treating investigator. These patients will be followed for survival at six month intervals for up to 5 years.

All patients will be followed for 5 years following last date of treatment:

- For patients in the study not requiring surgery following chemotherapy, the last day of treatment will be considered the last day of mFOLFOX therapy.
- For patients who receive short course radiation, the last day of treatment will be considered the last day of radiation.
- For patients in the TME group, the last day of treatment will be considered the day of surgery.

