10.2 Secondary Endpoints

Secondary outcomes of our study will include the analysis of safety and toxicity, disease free survival, and overall survival from data included up to five years after enrollment in the study. Data will be stored in the RedCap database.

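### Section 10.3's two reporting groups omit planned TME patients and early removals without surgery; if DFS and OS are also split, the responder curve carries guaranteed time

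*Combined protocol and SAP*

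**What the plan says.** Section 10.3 lists, in order, the response rate with its confidence interval, DFS and OS ("Disease-free and overall survival will be described using the Kaplan-Meier method"), adverse-event tables, and QOL ("Changes in QOL (from baseline) will be described using means and standard deviations at each time point assessed"). It then says "We will calculate these summary measures separately in those who obtain a complete or near complete response to up to 12 cycles of mFOLFOX"; this first group also has the radiation and enters surveillance. The other group is "those who required surgery with or without radiation therapy prior to completion of mFOLFOX therapy".

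Section 3.0 puts surgery at the end of the planned sequence: 10 to 12 cycles, restaging, radiation, a further assessment, and then "Patients with a partial response or stable disease will undergo TME". Patients with stable or progressive disease at the interval assessment, after six cycles, leave the study (sections 3.0 and 5.4).

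No section defines a DFS event, or a time origin for DFS or OS. Section 10.2 refers to "disease free survival, and overall survival from data included up to five years after enrollment in the study". Section 3.0 says "All patients will be followed for 5 years following last date of treatment". No landmark or other handling of time before response is described.

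**The concern.** Two things are at stake.

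The first is coverage. The study asks how many patients can be spared surgery, so a reader will want outcomes for those who were spared it and those who were not. If the second group holds only patients operated on before finishing mFOLFOX, it leaves out the patients who completed the regimen and then had TME. Footnotes to Tables 3 and 4 say QOL is assessed on all patients, including those who stop after cycle 6 and those who go to surgery. Data would therefore be collected with no group to report them in.

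The second is conditional. If the split extends to DFS and OS, one group is defined by an event late in treatment. A patient must reach the post-radiation assessment alive, and without progression, to count as a responder. A responder curve that starts earlier includes a period in which it cannot fall. One-year DFS is a named secondary objective (section 2.2), and this period takes up much of that year.

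**Working it through.** **Step 1: who falls where.** Patient paths from sections 3.0, 5.4 and 5.6, against the wording of 10.3:

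- Complete or near complete response after chemotherapy and radiation, entering surveillance: first group.
- TME after chemotherapy and radiation: mFOLFOX is already complete, so neither group.
- Removed at the interval assessment, then surgery: second group.
- Removed or discontinued early, no surgery: neither group.

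The timing qualifier could instead attach only to the radiation. The second group could then take in the later TME patients, but the wording would describe radiation before the end of chemotherapy, which the protocol schedule does not contain. Patients removed without surgery would still have no group.

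**Step 2: when responders are identified.** Inputs: 14-day cycles dosed on day 1 (5.3); 10 to 12 cycles (3.0); restaging 4 to 12 weeks after last chemotherapy and assessment 6 to 12 weeks after radiation (Table 3); radiation over 5 days (5.3), taken as 1 week and assumed to follow restaging directly.

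Week from C1D1 = 2 × (cycles − 1) + restaging gap + 1 + post-radiation gap.

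- Minimum: 18 + 4 + 1 + 6 = 29 weeks.
- Maximum: 22 + 12 + 1 + 12 = 47 weeks.

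This is 29/52.18 = 56% to 47/52.18 = 90% of the first year. Counting the last cycle in full gives 31 to 49 weeks; applying the visit windows gives about 27 to 48. From enrollment, the pretreatment interval is added: up to 45 days, or 60 with its window (8.6 weeks), so at most about 56 weeks.

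**Step 3: size against an unselected cohort.** The plan gives no figure to reproduce. Assume a constant hazard h, the same for everyone, with time from C1D1. Then 1-year DFS is exp(−h) overall and exp(−h(1 − g)) in a group guaranteed event-free to g = weeks/52.18.

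- Cited 68% 5-year DFS (1.2): h = −ln(0.68)/5 = 0.0771. Overall 92.6%; responders 96.6% (29 weeks) to 99.2% (47 weeks). Inflation 4.1 to 6.7 points.
- Cited 67.9% 3-year DFS (1.2, the six-cycle FOLFOX pilot): h = −ln(0.679)/3 = 0.1290. Overall 87.9%; responders 94.4% to 98.7%. Inflation about 6.5 to 10.8 points (6.6 to 10.9 with a 52-week year).

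**Step 4: if time runs from last treatment.** For irradiated patients without surgery this is the last day of radiation (3.0), so the guaranteed time is 6 to 12 weeks. With h = 0.0771, a group guaranteed 6 or 12 weeks shows 93.4% or 94.2% at 1 year, an inflation of 0.8 to 1.7 points.

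**Step 5: the surgical patients.** They must also survive to surgery. C6D1 is week 10 and the interval assessment falls within 14 days of it, about week 12. If patients operated on after early removal are guaranteed 12 weeks, the Step 3 formula with h = 0.0771 gives 94.2%. The gap to responders is then 96.6 − 94.2 = 2.4 to 99.2 − 94.2 = 5.0 points. TME after the post-radiation assessment carries at least as much guaranteed time from C1D1 as a response does, so there the gap can vanish or reverse.

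**The case against.** The strongest reply is that only QOL is split. The sentences on either side concern QOL, means and standard deviations are summary measures in the plain sense, and the response rate in the same list cannot be split by response. On that reading there is no survival bias. This is a fair reading, but the text does not settle it: an analyst could also produce Kaplan-Meier curves by group. The coverage gap remains either way.

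Next, section 10.2 limits the data used rather than setting a time origin, and follow-up in section 3.0 runs from last treatment. That stands. It reduces the guaranteed time to 6 to 12 weeks but does not remove it.

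Third, little depends on these curves. The schema includes all patients in the evaluation of overall survival, the Kaplan-Meier sentence names no subgroup, no test between groups is planned, and the primary endpoint keeps patients who stopped for stable or progressive disease in its denominator. All of this stands and limits the consequence.

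A reader might infer that the plan gives watch-and-wait a head start of 29 to 47 weeks over surgery. The documents do not support that: surgical patients carry guaranteed time too. A reader might also assume a lower 1-year DFS, such as 80%, and obtain a larger effect. Under a constant hazard that implies 0.8^5 = 33% at 5 years, about half the 65 to 68% cited in section 1.2.

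**Conclusion.** The coverage defect holds whichever measures are split: as worded, the second group excludes the planned TME patients, and early removals without surgery have no group.

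The guaranteed-time problem holds only if DFS and OS are among the split measures. The guarantee is strict for OS. For DFS it depends on an event definition that the plan does not give, in patients who enrol with tumor in place. The sizes in Step 3 rest on a constant, equal hazard, on time from C1D1 and on DFS figures from other cohorts. They measure inflation against an unselected cohort and are not an estimate of bias between the two groups. The conclusion that the plan necessarily favours non-operative management is not supported. This is a wording change worth making before analysis; the primary result does not depend on it.

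**What to change.** In section 10.3:

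1. Define groups that cover everyone: complete or near complete response entering surveillance; TME after completing chemotherapy and radiation; all remaining patients, chiefly those removed or discontinued earlier. Section 3.0 sends stable disease to TME but removes patients with less than 20% response, while section 10.1 defines stable disease by that same threshold. These passages must be reconciled so that each patient's group is clear.
2. State which measures are split. If only QOL, say so.
3. Define the DFS event, and report DFS and OS for all patients as one curve from C1D1. Start any by-group DFS or OS curve at the post-radiation assessment, among patients event-free then. Guaranteed time is then zero by construction.

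This needs no new visits, data or patients. The cost is that early failures appear only in the all-patient survival curve, and that the groups are small: at the anticipated 30% response, 0.30 × 40 = 12 responders.
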